8.3.3. Antibody Secreting Cells (Plasmablasts)

Due to the requirement for freshly isolated PBMCs, the plasmablast (antibody secreting cell [ASC]) assay will be performed only on specimens collected from subjects enrolled at Emory Children's Center and the Hope Clinic of Emory Vaccine Center. Values below the lower limit of detection will be handled as described in Section 4.5.2. The frequency of strain-specific 2013 and 2017 A/H7N9 IgA, and IgG ASCs will be summarized for the mITT and PP populations by study group at 8 days post each study vaccination. Descriptive summary statistics will be provided for both time points including the number of subjects with non-missing results, mean, standard deviation and corresponding 95% CI as well as median, minimum and maximum values. Geometric mean and 95% CI may also be assessed depending on the observed distribution of the data. Summaries are presented for the 2013 A/H7N9 strain in [Table 80](#) and for the 2017 A/H7N9 strain in [Table 81](#).

Box and whisker plots will summarize the distribution of ASC results for each immunoglobulin type, strain, and study day ([Figure 12](#), [Figure 13](#), [Figure 14](#), [Figure 15](#), [Figure 16](#), [Figure 17](#)). Scatterplot matrices depicting the relationship and correlation between immunoglobulin types for the strain-specific ASCs at the same day, as well as between the same immunoglobulin types post each study vaccination, will be shown in [Figure 18](#), [Figure 19](#), [Figure 20](#), [Figure 21](#), [Figure 22](#), [Figure 23](#), [Figure 24](#) and [Figure 25](#). Strain-specific ASC frequency at 8 days post vaccination will also be correlated with HAI and Neut titer at 21 days post vaccination as shown in [Figure 22](#), [Figure 23](#), [Figure 24](#), and [Figure 25](#). The statistician will determine if the Pearson or the Spearman Rank-Order correlation is appropriate at the time of analysis.

8.3.4. Other Assays

Descriptions of the NA assays and all other exploratory assays and the associated planned analyses will be described in an addendum to this SAP.

9. SAFETY EVALUATION

All summaries and analysis of safety data will be presented for the Safety Analysis Population. Safety summaries will be presented overall and grouped by study group.

Continuous variables will be summarized using the following descriptive statistics: n (non-missing sample size), mean, standard deviation, median, maximum and minimum. All categorical measures will be summarized by the frequency and percentages of observed levels will be reported for all categorical measures. The denominator for the percentages may be based on the number of non-missing observations for an assessment or based on the number of subjects in a population. This will be described for each table.

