3 STUDY OBJECTIVES AND OUTCOME MEASURES

3.1 Study Objectives

3.1.1 Primary

Safety:

- To assess the safety and reactogenicity of 2013 and 2017 A/H7N9 IIVs given with or without AS03 adjuvant following receipt of each study vaccine.

Immunogenicity:

- To assess the serum hemagglutination inhibition (HAI) and neutralizing (Neut) antibody responses following receipt of the second study vaccine.

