11.4.3 Sample Size

This study is planned to enroll up to 180 subjects. The sample size for this study was selected to obtain preliminary estimates in a time critical manner. While this study is not designed to test any specific null hypothesis, the following illustrates the precision and power that are available for select estimates and comparisons of interest.

[Table 12](#) indicates the probability of observing one or more safety events, such as solicited injection site or systemic reactogenicity events or an unsolicited non-serious AE of a particular type for a single treatment arm (N=30), or in the trial as a whole (N=180).

Table 12: Power (%) to Detect Safety Events

Event Frequency	N=30	N=180
≥10% Very Common	95	>99
≥1% Common	26	83
≥0.1% Uncommon	2	16
≥0.01% Rare	<1	1

Binomial confidence intervals (CI) are widest (have the least precision) when the response rate is 50%. [Table 13](#) is presented to indicate the worst-case scenario for precision of observed exact (Clopper-Pearson) binomial confidence intervals.

Table 13: Precision of Binomial Confidence Intervals

N	95% CI
30	31-69
180	42-58

[Table 14](#) illustrates the minimum detectable differences in the proportion of subjects responding (e.g. attaining seroconversion or a titer $\geq 1:40$) between any two treatment arms (N=30) using a two-sided Likelihood Ratio Test and $\alpha = 0.05$. It is assumed that up to 10% of subjects (N=3) will be excluded from the per protocol analysis. Seroconversion rates of 10% to 50% are considered.

Table 14: Minimum Detectable Difference in Proportion Responders

N per Group	Proportion Responders in Comparator Group A	80% Power	
		Minimal Detectable Difference	Proportion Responders in Comparator Group B
N=27	0.10	0.32	0.42
	0.20	0.35	0.55
	0.30	0.38	0.68
	0.40	0.37	0.77
	0.50	0.34	0.84

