4. INVESTIGATIONAL PLAN

4.1. Overall Study Design and Plan

DMID Protocol 17-0078 follows a Phase II randomized, partially-blinded study design enrolling males and non-pregnant females aged 19 to 50 years of age, inclusive, who are in good health as determined by medical history and physical examination, and meet all eligibility criteria, including erythrocyte sedimentation rate (ESR), hematology, and biochemistry parameter within acceptable range, and negative urine or serum pregnancy test (for females). This clinical trial is designed to assess the safety, reactogenicity and immunogenicity of one or two vaccinations of monovalent inactivated split influenza 2013 and 2017 A/H7N9 virus vaccines (2013 and 2017 A/H7N9 IIVs) manufactured by Sanofi Pasteur (SP), administered intramuscularly at different dosages (3.75 or 15 mcg of HA per dose), given with or without AS03 adjuvant manufactured by GlaxoSmithKline Biologicals (GSK), using different heterologous and homologous prime-boost vaccination schedules.

Subjects will be randomly assigned to 1 of 6 study groups with equal allocation 1:1:1:1:1:1 (see [Table 1](#)). Subjects assigned to Groups 1, 2, and 3 will receive an adjuvanted 2013 A/H7N9 IIV on Day 1 while those in Groups 4, 5, and 6 receive an adjuvanted 2017 A/H7N9 IIV on Day 1. Subjects assigned to Groups 1 and 4 will return approximately 21 days after their first vaccination to receive an adjuvanted 2017 A/H7N9 IIV. Subjects assigned to Groups 2,3,5, and 6 will return approximately after 120 days to receive their second vaccination of 2017 A/H7N9 IIV with or without AS03.

Reactogenicity will be measured by the occurrence of solicited injection site and systemic reactions from the time of each study vaccination through 7 days after each study vaccination. Unsolicited non-serious AEs will be collected from the time of each study vaccination through approximately 21 days after each study vaccination. SAEs and MAAEs, including NOCMCs and PIMMCs, will be collected from the time of the first study vaccination through approximately 12 months after the last study vaccination. Clinical laboratory evaluations for safety will be performed on venous blood collected prior to each study vaccination and approximately 7 days after each study vaccination.

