4.4.4. Selection of Doses in the Study

Subjects in Groups 1, 2, and 3 are to receive a first vaccination of AS03 adjuvanted 2013 A/H7N9 IIV at HA dose of 3.75mcg, and a second vaccination of either AS03 adjuvanted 2017 A/H7N9 IIV at HA dose of 3.75mcg (Groups 1 and 2) or unadjuvanted 2017 A/H7N9 IIV at HA dose of 15mcg (Group 3). Subjects in Groups 4, 5 are to receive two AS03 adjuvanted 2017 A/H7N9 vaccinations at HA doses of 3.75. Subjects in Group 6 are to receive a first vaccination of AS03 adjuvanted 2017 A/H7N9 IIV at HA dose of 3.75mcg, and a second vaccination of unadjuvanted 2017 A/H7N9 IIV at HA dose of 15mcg.

The 3.75 mcg with AS03 dose was selected to evaluate safety and immunogenicity of antigen sparing dose strategies compared to that of using a higher dose of 15 mcg without adjuvant. Using the 2013 and 2017 A/H7N9 IIVs allows the evaluation of priming effects of different A/H7N9 IIVs.

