5. SAMPLE SIZE CONSIDERATIONS

This study is planned to enroll up to 180 subjects. This study is not designed to test a formal null hypothesis. Rather, it is intended to obtain sufficient data to obtain meaningful estimates of the immune response and to uncover any safety issues that occur at a sufficiently high rate that they might be observed in a study of this size. As such, the type I error rate, $\alpha = 0.05$, is not adjusted for multiple comparisons. While this study is not designed to test any specific null hypothesis, the following tables illustrate the precision and power that is available for select estimates and comparisons of interest.

[Table 6](#) indicates the probability of observing one or more safety events, such as solicited injection site or systemic reactogenicity events or an unsolicited non-serious AE of a particular type for a single study group ($N = 30$), or in the trial as a whole ($N=180$).

Binomial confidence intervals (CI) are widest (have the least precision) when the response rate is 50%.

[Table 7](#) is presented to indicate the worst-case scenario for precision of observed exact (Clopper-Pearson) binomial confidence intervals.

[Table 8](#) illustrates the minimum detectable differences in the proportion of subjects responding (e.g. attaining seroconversion or a titer $\geq 1:40$) between any two study groups ($N=30$) using a two-sided Likelihood Ratio Test and $\alpha = 0.05$. It is assumed that up to 10% of subjects ($N=3$) will be excluded from the per protocol analysis. Seroconversion rates of 10% to 50% are considered.

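### The primary safety objective is per vaccine after each dose, but no pooled first-dose rate by product, and no first-dose-only 2013 v 2017 contrast, is planned

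*SAP*

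**What the plan says.** Protocol 3.1.1 gives the primary safety objective as "To assess the safety and reactogenicity of 2013 and 2017 A/H7N9 IIVs given with or without AS03 adjuvant following receipt of each study vaccine". SAP 3.1.1 repeats it.

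On presentation, SAP 9 states "Safety summaries will be presented overall and grouped by study group". SAP 6.1 fixes one column per study group, and Protocol 11.6.2 summarises solicited events by treatment arm for each vaccination and overall.

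On what is given, subjects are "randomly assigned to 1 of 6 study groups with equal allocation 1:1:1:1:1:1" (SAP 4.1). At the first dose, "Subjects assigned to Groups 1, 2, and 3 will receive an adjuvanted 2013 A/H7N9 IIV on Day 1", and "those in Groups 4, 5, and 6 receive an adjuvanted 2017 A/H7N9 IIV on Day 1". Table 1 in both documents shows the same dose and adjuvant, 3.75 mcg+AS03, in all six arms on Day 1. At the second dose, Table 1 shows 2017 3.75 mcg+AS03 in Groups 1, 2, 4 and 5, and 2017 15 mcg without AS03 in Groups 3 and 6.

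SAP 9.3.1 also plans a logistic model with prime-boost combination, boost dose and interval terms for any local and any systemic event (Tables 87 and 88).

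**The concern.** The unit of the objective is a product after a dose. The unit of the descriptive tables is a two-dose regimen. After dose 1 the regimens have not yet diverged within Groups 1-3 or within Groups 4-6, so the arm split divides people who received the same product. The All Subjects figure does not repair this, because it combines the 2013 and 2017 antigens at dose 1, and adjuvanted with unadjuvanted vaccine at dose 2.

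At stake is the precision of the basic reactogenicity rate for each product. The randomised comparison of the two antigens after a first dose is also at stake: it is the cleanest safety contrast the design offers, and no planned analysis clearly isolates it.

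**Working it through.** **Inputs.** Planned 30 per arm and 180 in all (Table 1; SAP 5). Identical first doses: 3 x 30 = 90 for 2013+AS03 and 3 x 30 = 90 for 2017+AS03. At dose 2, on Table 1: 4 x 30 = 120 adjuvanted and 2 x 30 = 60 unadjuvanted. No dropout is assumed.

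**Reproducing the plan's figures.**
- Chance of at least one event, 1-(1-p)^N. At p=1%: 1-0.99^30 = 26.0% and 1-0.99^180 = 83.6%. SAP Table 6 (Protocol Table 12) shows 26 and 83, so it drops the decimals.
- Clopper-Pearson 95% interval at half the subjects: 31.3-68.7% for N=30 and 42.5-57.5% for N=180. SAP Table 7 shows 31-69 and 42-58.

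**The same quantities by product received.**

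| N | Worst-case 95% CI | Upper limit, zero events | Chance of seeing a 1% event |
|---|---|---|---|
| 30 (one arm) | 31.3-68.7% | 11.6% | 26.0% |
| 60 (unadjuvanted boost) | 36.8-63.2% | 6.0% | 45.3% |
| 90 (each first-dose product) | 39.3-60.7% | 4.0% | 59.5% |
| 120 (adjuvanted boost) | 40.7-59.3% | 3.0% | 70.1% |

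The zero-event limit is 1-0.025^(1/N). The worst-case interval is 37.4 points wide at N=30 and 21.5 at N=90, and 37.4/21.5 = 1.7.

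**Detectable difference.** Pooled-variance z test, two-sided 0.05, 80% power, with an assumed 30% comparator rate (the documents give no reaction rate). It is 0.355 for 30 v 30 and 0.204 for 90 v 90. Over assumed rates of 10%, 20%, 30% and 50%, it runs from 0.309 to 0.355 for 30 v 30 and from 0.160 to 0.204 for 90 v 90.

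**Is first-dose pooling clean?** Allocation is randomised and the product is identical within each set of three arms. Each set has one 21-day arm and two 120-day arms, so planned interval is balanced between the pools. The second dose falls 21 to 28 days after the first at the earliest (SAP 4.4.5), so the 7-day and 21-day windows precede or end at it.

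**Does the model supply the answer?** Tables 87 and 88 report odds ratios, not rates. They cover any-local and any-systemic events, with individual symptoms modelled only if an effect is significant. The text of SAP 9.3.1 takes events after either vaccination, while both table titles refer to the period after the second; neither is dose 1 alone. Also, with the interactions in the formula and the shell's reference levels (15 mcg, 21 days), the prime-boost main effect describes a 15 mcg boost at 21 days, which no arm receives.

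**Second-dose pools.** On Table 1 the 120 are half 21-day (Groups 1, 4) and half 120-day (Groups 2, 5), while the 60 are all 120-day. A direct comparison mixes formulation with interval. AS03 also goes with 3.75 mcg and its absence with 15 mcg, so adjuvant and antigen amount cannot be separated. Within the 120-day arms, Groups 2, 5 v 3, 6 gives 60 v 60, with a detectable difference of 0.251 at the same assumed 30%.

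**Label conflict.** SAP 4.4.4 says "Subjects in Groups 4, 5 are to receive two AS03 adjuvanted 2017 A/H7N9 vaccinations at HA doses of 3.75", and Table 1 agrees, but the group list in SAP 6.1 labels Group 4's second dose as 2013. Group 4's first dose is 2017 throughout, so first-dose pooling is unaffected.

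**The case against.** The best reply is that the SAP follows the protocol, which specifies summaries by treatment arm, and that the trial is declared estimation-only with N=30 and N=180 precision disclosed. Each column of Tables 85 and 86 is already a rate for one product after one dose, with an exact CI, and a reader could add three columns. Tables 87 and 88 fit all arms together. On Table 1 every boost is 2017, so the prime-boost term is a prime-strain contrast, and events after either vaccination would include first-dose events. Protocol 11.6.2 also permits chi-square or Fisher tests between arms.

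Much of this stands. A reader might infer that every safety table is split by arm, or that no vaccine-level rate is estimated at all; Tables 85-88 show otherwise. A reader might also say that two thirds of the precision is lost. One third of the sample sits in each column, but the worst-case interval is 1.7 times wider, not three times.

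What does not stand is that the gap is closed. Adding counts by hand is not a planned estimate with a CI, arm-to-arm tests remain 30 v 30, and the model neither yields rates nor isolates dose 1.

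**Conclusion.** The point holds for descriptive summaries and for the first dose. The objective is per vaccine after each dose, yet no pooled product rate with a CI is planned, and no first-dose-only 2013 v 2017 contrast is clearly planned. Using 90 rather than 30 narrows the worst-case CI from 31-69% to 39-61%, lowers the zero-event limit from 11.6% to 4.0%, and raises the chance of seeing a 1% event from 26% to 60%. The detectable difference falls from 0.355 to 0.204 at the assumed 30% rate. These figures assume full planned enrolment.

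This is a change that should be made. It does not invalidate the arm-level tables, which remain correct for regimens. A reader might infer that the second-dose pools allow a clean adjuvant comparison; they do not, because interval and antigen amount differ with formulation. A reader might also ask for the event-detection table in the sample size section to be restated. Its truncation changes entries by less than one point and needs no action.

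One minor slip is real: in the shell for Table 122, whose format Tables 123 and 124 share, the All Subjects block omits Day 8 after the first vaccination and lists the pre-dose-2 sample twice. Table 115 has the expected rows.

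**What to change.** 1. Add pooled by-product summaries to the post-dose-1 displays: 2013+AS03 (Groups 1-3) and 2017+AS03 (Groups 4-6), each with an exact 95% CI, plus their difference with a 95% CI. Use extra columns in Tables 85 and 90. Use extra row blocks in Table 93, the post-vaccination-1 part of Tables 102-105 and the Day 8 post Vac 1 laboratory tables, where groups run down the page. Keep the six arms.
2. If dose 2 pools are added (planned 120 and 60), label them descriptive. Make any formulation contrast within the 120-day arms (Groups 2, 5 v 3, 6) or adjust it for interval, and state that adjuvant and antigen amount change together.
3. Reconcile the outcome period for Tables 87 and 88 between the SAP 9.3.1 text and the table titles.
4. Reconcile the Group 4 second-dose label in SAP 6.1 with SAP 4.4.4 and Table 1 before any dose 2 pooling.
5. In the All Subjects rows of Tables 122-124, restore Day 8 post Vac 1 and remove the duplicate pre-dose-2 row.

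The cost is SAP wording and shell programming. Sample size, visits and data collection do not change.

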9.1. Demographic and Other Baseline Characteristics

Summaries of age, sex, ethnicity, race, BMI, and prior receipt of seasonal influenza vaccine will be presented by site ([Table 19](#), [Table 20](#)) and by study group ([Table 21](#), [Table 22](#)). Age will be summarized as a continuous variable. Ethnicity is categorized as Hispanic or Latino, or not Hispanic and not Latino. In accordance with NIH reporting policy, subjects may self-designate as belonging to more than one race or may refuse to identify a race, the latter reflected in the electronic case report form (eCRF) as “No” to each racial option. BMI will be summarized as a continuous as well as categorical variable, categorized as (<30, ≥30). Self-reported history of prior receipt of influenza vaccines will be broken down by the following categories: receipt of seasonal vaccines for prior seasons (2016-2017, 2017-2018), receipt of seasonal vaccine for the current season (2018-2019; considered up to receipt of study dose 2), and receipt of any A/H5 vaccines prior to enrollment. Demographic information for individual subjects will be provided in [Listing 6](#). Subjects’ prior influenza vaccination history (seasonal and non-seasonal) will be provided in [Listing 8](#).

9.1.1. Prior and Concurrent Medical Conditions

All current illnesses and past or pre-existing medical conditions will be coded using Medical Dictionary for Regulatory Activities (MedDRA) version 20.0 or higher.

Summaries of subjects’ prior and concurrent medical conditions will be presented by study group ([Table 23](#)).

Individual subject listings will be presented for all reported medical history including prior and concurrent medical conditions ([Listing 7](#)).

9.1.2. Prior and Concomitant Medications

Concomitant medications will be coded to the Anatomical Therapeutic Classification using the WHO Drug Dictionary. The use of concomitant medications during the study will be summarized by ATC1 and ATC2 code and study group for the Safety population ([Table 132](#)). A listing of concomitant medications will be presented ([Listing 18](#)).

9.2. Measurements of Treatment Compliance

All subjects are to receive 2 study vaccinations administered in the clinic. The number of study vaccinations administered to subjects will be presented by study group in [Table 17](#) and [Table 18](#) and as part of the subject disposition tables ([Table 16](#)). [Listing 1](#) presents subjects who received investigational product with study group and study product received for each vaccination.

9.3. Adverse Events

A summary of all adverse events is provided in [Table 82](#). A summary of those events that occurred in $\geq 5\%$ of subjects in any study group is provided in [Table 83](#).

9.3.1. Solicited Events and Symptoms

Systemic solicited adverse events were collected pre-vaccination, and systemic and local solicited adverse events were collected at-least 20 minutes post-vaccination and then daily for 7 days after each vaccination and graded on a scale of 0 (absent), 1 (mild), 2 (moderate) and 3 (severe). Systemic events include fever, feverishness, fatigue, malaise, myalgia, arthralgia, headache, and nausea. The grading scale for systemic events, including quantitative grading for fever, is included in [Table 11](#). Local events include pruritus, ecchymosis, erythema, induration/swelling, pain, and tenderness. Ecchymosis, erythema, and induration are measured by both functional and measurement grading scales as defined in [Table 10](#).

When calculating the incidence of solicited events, each subject will be counted once at the highest severity following the applicable vaccination, and any repetitions will be ignored. For summaries presented separately for each vaccination, the denominator for percentages will be the number of subjects who received the respective vaccination with non-missing data for the event summarized. For summaries over all vaccinations the denominator will be the number of subjects who received at least one vaccination with non-missing data for the event summarized.

The number and percentage of subjects reporting at least one solicited adverse event of each severity will be summarized for each solicited symptom, any systemic symptom, any local symptom, and any symptoms. For each event the denominator is the number of subjects who received the applicable vaccination with non-missing data for the specific event. The 95% CI calculated using Clopper-Pearson methodology from a binomial distribution (SAS Proc Freq with a binomial option) will be presented ([Table 84](#), [Table 85](#), [Table 86](#)). Logistic regression models will be fit to estimate the effect of prime-boost combination (*PrimeBoost*), Boost dose (*BoostDose*), and interval between vaccinations (*Interval*) on the probability of reporting any local event or reporting any systemic event after either vaccination ([Table 87](#), [Table 88](#)). If statistically significant effects are observed in the model for local events or systemic events, then additional models will be fit for each individual event of that type.

$$\text{logit}[P(\text{Event})] = \beta_0 + \beta_1 \times \text{PrimeBoost} + \beta_2 \times \text{BoostDose} + \beta_3 \times \text{Interval} + \beta_4 \times (\text{PrimeBoost} * \text{BoostDose}) + \beta_5 \times (\text{PrimeBoost} * \text{Interval}) + \varepsilon,$$

For each systemic and local event, any systemic event, any local event, and any solicited event, the maximum severity over 7 days after each vaccination will be summarized for the Safety population. The number and percentage of subjects reporting each event will be summarized by the maximum severity and study group, separately for each vaccination and over both vaccinations. For each event the denominator is the number of subjects who received the applicable vaccination with non-missing data for the specific event. The 95% CI calculated using Clopper-Pearson methodology from a binomial distribution (SAS Proc Freq with a binomial option) will be presented ([Table 89](#), [Table 90](#), [Table 91](#)).

The number of subjects reporting a solicited adverse event will be summarized for each day post vaccination for each vaccination and for both vaccinations combined both in a summary table ([Table 92](#), [Table 93](#), [Table 94](#)) and graphically in a bar chart ([Figure 26](#) and [Figure 27](#)). A comparison of the event rate for each study group between study vaccinations will be presented, including p-values from McNemar's test performed ([Table 95](#), [Table 96](#)).

Systemic and Local solicited events reported by subject will be presented in [Listing 11](#) and [Listing 12](#), sorted by subject ID, vaccination number, parameter, and study day.

